10.3 Accrual Rate and Duration

Based on our experience we plan to enroll 45 patients per year. It will take approximately 2.0 years to complete the enrollment of 88 patients. Given the relatively

short follow-up time (90 days), all patients will be followed for up to 90 days once enrolled.

10.4 General Statistical Plan

Patients enrolled will be presented. On-study protocol violations will also be presented. Patients who do not complete the required observations will be listed and evaluated separately as necessary. Reasons for study discontinuation and date of withdrawal from study will be presented.

Descriptive statistics related to the participant characteristics, treatment, and prognostic factors will be reported. For the continuous variables mean (95% confidence interval), median (minimum and maximum) will be reported and for discrete variables frequency and percentages will be reported. For continuous variables a two sample t-test/rank sum test will be used to compare between groups. A Chi-square test will be used for establishing association between categorical variables. For example MoCA will be compared between two groups using a contrast based t test in addition to simple two sample test either based on a linear regression or Mixed model approach when multiple observations on sample subject is considered. A discrete outcome such as prevalence of 'have any fever' between treatment and control arms will be tested using a logistic regression analyses. In order to examine the significant prognostic factors, we will use the multiple linear and logistic regression models in multi-variable setting.

A significance level of 5% will be used to declare results significant. For selected primary outcome variables we will report adjusted p-values for multiplicity in addition to unadjusted p-values. All calculations will be performed with methods described in Walker et al. (2010), Rosner (2010) and with SAS statistical software (SAS, 2003).

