STUDY POPULATION	
Patients with a supratentorial aSAH secondary to a ruptured cerebral aneurysm that has been secured by endovascular coil embolization. Study subjects must score as a WFNS SAH grade ≤ 2 post-coiling with no significant aphasia at the time of enrollment and have a significant hemorrhage burden on the initial head computed tomographic (CT) scan that demonstrates a modified-Fisher grade 3, or grade 4 (with minimal intraparenchymal blood or IVH less than 25%.)

CLINICAL SITES	
Eight to ten designated clinical sites in the USA.

PLANNED ENROLLMENT	
88 patients (44 in each treatment allocation group; Approximately 5-6 patients per site per year average)

STUDY DURATION	
3 years [2 years enrollment; 3 months primary end-point follow-up visit; 3 months data analysis and reporting of results; 1-year follow-up visit secondary endpoint].

PRIMARY SAFETY ENDPOINT	
Rate of “Major Bleeding” or “Clinically Relevant Non-Major Bleeding” as defined by the International Society of Thrombosis and Haemostasis (ISTH) between the groups from enrollment until discharge from the acute inpatient setting.

SECONDARY SAFETY ENDPOINT	
Rate of Symptomatic Intracranial Hemorrhage between the two groups from enrollment until discharge from the acute inpatient setting. A symptomatic hemorrhage is defined as a 4-point or greater increase in the NIHSS or a decrease in the GCS by 2 or more points not explained by other causes.

ADDITIONAL PRESPECIFIED SAFETY OUTCOMES TO BE ANALYZED	
Rate of any new intracranial hemorrhage between the two groups from enrollment until discharge from the acute inpatient setting.
 
Rate of Serious Adverse Events (SAEs) between the two groups from enrollment until

the 90-day follow-up visit as reported by each site and adjudicated by an independent Clinical Events Adjudication Committee (CEC).

Rate of Type II Heparin Induced Thrombocytopenia (HIT) between the two groups from enrollment until the 90-day follow-up visit

Rate of DVT or PE between the two groups from enrollment until the 90-day follow-up visit

All cause and neurological mortality rates between the two groups from enrollment until the 90-day follow-up visit

PRIMARY CLINICAL EFFECT ENDPOINT

Mean Montreal Cognitive Assessment score (MoCA) at 90 (± 10) days post enrollment.

SECONDARY ENDPOINTS:

-PRIMARY BIOMARKER ENDPOINT

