Peak and Overall Plasma and CSF levels of hsCRP at enrollment and, infusion days #2, 4, 6, and 10 compared between groups.

-SECONDARY CLINICAL EFFECT ENDPOINTS

Trail Making Test Parts A&B at 90 (± 10) days post enrollment.

MoCA at 1-year (± 30 days)

Center for Epidemiologic Studies Depression Scale (CES-D) at 90 (± 10) days post enrollment

Return to work status between groups at 90 (± 10) days

SECONDARY EXPLORATORY PRESPECIFIED BIOMARKER OUTCOMES

Plasma and CSF levels of IL-6, TNF- α , P-Selectin, sICAM-1, HMGB-1, MRP8/14 plasma levels at enrollment and infusion day #2, 4, 6, and 10

ADDITIONAL PRE-SPECIFIED

Rate of MoCA ≤ 20 between groups at the 90-day follow-up visit.

**EXPLORATORY
OUTCOME ANALYSES**

In-hospital incidence of any fever ($> 38.3^{\circ} \text{C}$; $\geq 101.0^{\circ} \text{F}$), Incidence of multiple fever episodes (≥ 3), and Mean Daily Fever Burden.

GCS and NIHSS at enrollment and infusion days # 2,4,6,10, discharge and 90 (± 10) days

MoCA at post-enrollment day #1, 6 and 10

Correlation analysis between MoCA scores and inflammatory biomarker levels with and without adjusting for hemorrhage burden (Hijdra Sum Score).

Incidence of moderate and severe Radiographic Cerebral Vasospasm based on a CTA, MRA, or Catheter DSA obtained between PBD # 6-12 as determined by an independent and blinded core imaging lab.

Incidence of TCD criteria for significant vasospasm (velocities $>200 \text{ cm/s}$ and / or MCA / ICA (Lindgaard) ratio >6)

Incidence of TCD criteria for absence of vasospasm (velocities $<120 \text{ cm/s}$)

Incidence of clinical vasospasm requiring rescue therapy (eg, pressors, endovascular treatment)

Incidence of "Delayed Cerebral Ischemia" defined as:

- Symptoms of neurological deterioration (e.g. hemiparesis, aphasia, decreased level of consciousness)
- Symptoms last for more than an hour
- Symptoms are not explained by other physiological processes (e.g., hydrocephalus, hypotension)

CT or MRI evidence of Vasospasm Related Cerebral Infarction on post-infusion (discharge) imaging as scored by an independent and blinded core imaging lab

Global outcome as measured between group ordinal regression analysis of the modified Rankin Scale score at 90-days and 1-year.
Return to work status between groups at 1-year.
Lawton IADLs at 90 (± 10) days
QOLIBRI-OS at 90 (± 10) days and 1-year.
Checklist Individual Strength-subscale Fatigue (CIS-f) at 90 (± 10) days
Barthel Index at 90 (± 10) days and 1-year

**INVESTIGATIONAL

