10. DATA ANALYSIS AND CONSIDERATIONS

10.1 Sample Size Justification and Primary Clinical Effect Analysis

The sample sizes justification is based on the combination of the pilot data that we have previously observed ([name] Unpublished) and results based on Schweizer et al. (2012). Two main outcomes, MoCA and MMSE, were compared by Schweizer et al (2012) and their validity was compared. The two measures have slightly different cut-offs for defining impairments (MoCA score <26 and MMSE score <27). In this study we will use MoCA as a primary outcome measure. Based on published data, MoCA has mean (SD) of 25.4 (2.8) with n=32. In our pilot data with small sample sizes, we observed an overall mean of 24.6 (5.4) with n=47. The separate group means were 26.4 (2.3) with n=25 and 22.7 (7.0) with n=22 in the treatment and control arms, respectively. Because the two groups were heterogeneous, we assume SD=2.5 in treatment group and SD=7.0 in control group. As hypothesized and as documented in the preliminary data, MoCA is higher in the treatment arm than in the control arm, and so we will use one-sided test procedures. The study design is that of a two group, multicenter randomized clinical trial.

Table S1: Sample sizes based on having alpha=5% and SD1=7.0 and SD2=2.5 to detect 3 unit (effect size=0.5 SD) using one-sided two-sample t test with unequal variances.

Power	N1	Total N
80%	40	80
85%	46	92
90%	54	108

Given the number of centers participating, we plan to enroll 40 evaluable subjects in each arm. Assuming 8 centers, a sample size of 80 would be realized by recruiting 10 per center. Note that we need to balance the number of treatment and controls to be equal at each center, but not necessarily having equal number of subjects at each center. However, the numbers in the tables do not adjust for loss to follow up, drop outs, the ability to adjust for covariates, or for the loss of degrees of freedom for the centers in a test or model. The discussion below addresses further aspects of the sample size consideration.

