Based on a desired total of 40 patients per arm, and an assumed dropout rate of 10%, the trial would require 44 patients in each arm for a total enrollment plan of 88 patients distributed over 8 sites, or on average 11 patients per site. There are multiple covariates that may confound the findings and this needs to be addressed in the design of the study. The primary factors are: center, risk associated with anterior communicating artery (ACoA) aneurysm location (1 versus others), age (≤ 70 versus > 70) and sex. The other factors are: fever (yes, no), transfusion (yes, no), vasospasm (yes, no). Due to limited resources only primary factors (ACoA, group and sex) will be considered to balance the allocation of treatment and control in 1:1 ratio. Thus, the randomization will be balanced within each of 6 strata. Advanced age will be controlled for by eliminating enrollment for patients over 70 years. Effect of the remaining factors will be addressed in the multi-variate model.

We will also compare the frequency of severe cognitive impairment (MoCA ≤ 20) in the two arms. Previous data demonstrated a rate of 0% (0/25) severe cognitive impairment in the heparin treatment group and approximately 32% (7/22) in the control group. In our currently planned study, we will assume a 5% rate of severe cognitive impairment in the heparin treatment group and a 32% rate of severe cognitive impairment in the control group. This will also allow a demonstration of power = 80% with alpha at 0.05 for our previously calculated sample sizes ($n_1=40$ and $n_2=40$) using a two-sample one-sided binomial test. This binomial calculation provides a second sample size estimate that supports our previous estimate of needing 40 patients per group. Therefore the final sample size estimation will be placed at a total of 88 patients to account for a 10% dropout rate leaving a final number of patients available for primary outcome analysis of 80 patients. Drop-out will be monitored during the enrollment process. If we approach 8 patients lost to follow-up then additional enrollments (beyond 88) will be considered if funding is available.

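### The 90-day MoCA comparison is planned on evaluable patients and gives death or neurological inability to be tested no value, so losses that differ by arm would bias it

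*Protocol*

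**What the plan says.** Protocol 1.1 defines the primary clinical effect endpoint as "Mean Montreal Cognitive Assessment score (MoCA) at 90 (± 10) days post enrollment". It lists "Rate of MoCA ≤ 20 between groups at the 90-day follow-up visit" among the exploratory outcomes.

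Protocol 10.1 sizes the trial on patients who have the measurement: "we plan to enroll 40 evaluable subjects in each arm". It then allows for losses ("an assumed dropout rate of 10%, the trial would require 44 patients in each arm") and arrives at 88 enrolled, "leaving a final number of patients available for primary outcome analysis of 80 patients". It also provides for replacement: "If we approach 8 patients lost to follow-up then additional enrollments (beyond 88) will be considered if funding is available".

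Protocol 10.4 adds: "Patients who do not complete the required observations will be listed and evaluated separately as necessary". The same section says that reasons for discontinuation will be presented, and it names t, rank-sum and mixed-model methods.

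No section says what value a patient contributes who has died by day 90 or is alive but neurologically unable to take the test. No section names an intention-to-treat set for the MoCA comparison.

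**The concern.** A MoCA score requires a patient who is alive, awake and able to communicate. After subarachnoid hemorrhage, some patients without a score will lack one because of a very bad outcome. Protocol 8.3 lists death, coma, stroke and aneurysm re-rupture among the anticipated complications. Heparin could plausibly move patients across the testable line in either direction, by preventing infarcts or by causing bleeds.

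A mean among testable survivors is then no longer a comparison of the groups as randomized. An arm that loses its worst patients shows a higher mean. An arm that keeps severely injured patients alive and testable shows a lower one. In the rate of MoCA of 20 or less, a dead or untestable patient is in neither numerator nor denominator. A significant improvement in mean MoCA is one of the two routes to study success in Protocol 1.1, and the test is one-sided, so a false advantage for LDIVH leads directly to a success claim.

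**Working it through.** **1. The plan's own figure.** Inputs from Table S1 in Protocol 10.1: "Sample sizes based on having alpha=5% and SD1=7.0 and SD2=2.5 to detect 3 unit", one-sided, unequal variances, 40 per arm.

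- Standard error = √(7.0²/40 + 2.5²/40) = √1.381 = 1.175.
- Noncentrality = 3/1.175 = 2.55, with about 49 Welch degrees of freedom.
- Power = 80.8%, and 40 is the smallest number per arm that reaches 80%.
- Allowance for dropout: 40 × 1.10 = 44 per arm, 88 in total.

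Table S1 reproduces. Its 80 are patients who still have a 90-day MoCA after dropout, so the sizing rests on completers.

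**2. How far a few patients can move a mean.** Inputs: pilot means of 26.4 (LDIVH) and 22.7 (control) from Protocol 10.1, and 44 per arm. Score 0 is an assumption made only to show scale.

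- One LDIVH patient: 26.4 × 1/44 = 0.60 points.
- Four LDIVH patients: 26.4 × 4/44 = 2.40 points.
- Four control patients: 22.7 × 4/44 = 2.06 points.
- Four in each arm: net shift 2.40 − 2.06 = 0.34 points.

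Four per arm is the protocol's total dropout allowance. The shift is large only if the losses are unbalanced.

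**3. Planned effect present among testable patients.** Assumed means among the testable are 25.7 and 22.7 (control pilot mean plus 3). The rates of MoCA of 20 or less are the protocol's 5% and 32%. Untestable patients score 0 for the mean and count as severe impairment for the rate.

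| Untestable, LDIVH vs control | Mean difference, all 44 per arm | Rate of MoCA of 20 or less |
|---|---|---|
| 0 vs 0 | 3.00 | 5% vs 32%, gap 27 points |
| 4 vs 0 | 25.7 × 40/44 − 22.7 = 0.66 | (0.05 × 40 + 4)/44 = 13.6% vs 32%, gap 18 points |
| 4 vs 4 | 25.7 × 40/44 − 22.7 × 40/44 = 2.73 | 13.6% vs (0.32 × 40 + 4)/44 = 38.2%, gap about 25 points |

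In all three rows the completers' comparison still shows 3 points and 27 percentage points.

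**4. No true effect.** In a simulation, both arms have 44 patients with scores drawn from a normal distribution with mean 22.7 and SD 7, rounded and limited to 0–30. The lowest scorers are removed, and the rest are compared by a one-sided unequal-variance t test at 5%.

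| Lowest scorers removed, LDIVH vs control | False benefit for LDIVH | One-sided rejection |
|---|---|---|
| 0 vs 0 | 0 | 5% |
| 2 vs 0 | 0.6 points | about 14% |
| 4 vs 2 | 0.5 points | about 14% |
| 4 vs 0 | about 1.2 points | about 25% |

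When both arms lose the same number, the bias is zero by symmetry.

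**5. Does the bleeding condition catch it?** Protocol 1.1 makes success conditional on no significant difference in major or clinically relevant non-major bleeding attributable to LDIVH. Protocol 8.5 puts the background rate at about 10–20%. With 44 per arm, a two-sided Fisher exact test at 5% detects a doubling with power of about 17% (10% vs 20%), 29% (15% vs 30%) or 45% (20% vs 40%). Four extra bleeds, 11 vs 7, give p = 0.43. The endpoint closes at acute discharge, whereas the MoCA is taken at 90 days. Deaths, infarcts and coma without bleeding are outside it.

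**The case against.** The strongest reply is that exclusion is inferred. No sentence says that dead or untestable patients leave the primary analysis. The sentence in 10.4 belongs to a paragraph on patient accounting, and its qualifier fixes no method. An SAP may exist and may set the rule. Section 3 distinguishes subjects who have expired from those who withdrew or were lost, so the protocol does not treat every missing patient alike. The methods in 10.4 include a rank-sum test, which could carry a worst rank, and a mixed model, which could use the inpatient MoCA scores of section 6.16. All of this is fair, and it limits how the point may be worded. It does not supply the missing value: neither method assigns one to death by itself, and what the protocol does state about sizing and setting aside points to completers.

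A reader might infer that fatal or disabling bleeds on heparin do not count against LDIVH at all. The documents do not support that. Under 8.5, fatal bleeding and symptomatic intracranial bleeding are major bleeding, which is in the primary safety endpoint and the success rule. Symptomatic intracranial hemorrhage, serious adverse events, mortality to 90 days and ordinal mRS are all prespecified in 1.1. The omission concerns the two MoCA measures only.

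A reader might also infer that a bias of 2 points or more is to be expected. That needs a 4 vs 0 split with every such patient scored 0, and the documents give no rate of death or untestability. The 21% infarction rate in section 2.2 comes from clipped patients and is not a rate of untestability. This trial enrolls coiled patients of WFNS grade 1–2 without aphasia. In the pilot controls, 7 of 22 scored 20 or below, so severely impaired patients could often be tested.

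**Conclusion.** The point holds for the mean MoCA and for the exploratory rate of MoCA of 20 or less. As the protocol stands, both compare patients who could be tested, and death or neurological inability contributes to neither.

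The size depends on imbalance between arms, which must be assumed. With no true effect, an excess of two to four untested lowest scorers on LDIVH produces a false benefit of roughly 0.5 to 1.2 points and a one-sided error of about 14% to 25%. These figures assume that the patients lost are exactly the lowest scorers, which is the unfavorable end. With equal losses there is little bias.

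The other safety and functional outcomes would show such events, but they do not correct the MoCA comparison. Of them, only bleeding enters the success rule, and that condition has low power and stops at discharge.

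**What to change.** Change Protocol 10.1 and 10.4 and the 90-day form as follows.

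- Record the reason for every missing 90-day MoCA: dead, neurologically unable to be tested, or other. The discontinuation reasons in 10.4 cover part of this already.
- In the severe-impairment comparison, count death and neurological inability as MoCA of 20 or less, with all such patients in the denominator.
- Prespecify a worst-rank analysis of the 90-day MoCA by rank-sum test: death lowest, then neurologically untestable, then observed scores. Handle scores missing for other reasons separately. Report it as a supporting analysis beside the mean. It need not become a further condition for success.

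The cost is one form field, a paragraph of text and one more analysis. The rates of MoCA of 20 or less become slightly less favorable. With four untestable patients in each arm, the one-sided power of that comparison is about 85% at 44 per arm, against 96% with none, and so still above the 80% stated in 10.1.

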6.4 Randomization Procedure

The randomization will be a blocked-stratified randomization scheme. We considered 4 factors for stratification to ensure equal distribution of factors between treatment groups: age, aneurysm location, gender, and clinical site. As age increases above 70 years old the risk for undiagnosed dementia increases and this could have a significant confounding result on our primary efficacy outcome of cognition (MoCA score). As a result we elected to limit enrollment to 70 years old or less to eliminate the need for age stratification. Given we will have 8-10 clinical sites, stratification of randomization by site would be difficult to implement while controlling for other more important factors and therefore we will do post-analysis statistical controlling for clinical site. Finally we elected to stratify with just two factors sex and aneurysm location. Aneurysm location will be a binary stratification of anterior communicating artery (ACoA) aneurysm versus all other locations. This was done because of previous reports that ACoA location SAH has a higher risk of cognitive disability than other locations and our own preliminary human data that suggests the same. Block sizes will fall within the range of 4-10 but will not be disclosed in this protocol to prevent any bias related to patient selection by investigators.

A member of the study team can randomize post-coiling subjects with informed consent who continue to meet the eligibility criteria. Patients will be randomized to one of two treatment allocation (LDIVH or Control) groups. A blocked-stratified randomization table will be created prior to initiation of the study. The REDCap database will utilize this to select treatment allocation. If the randomization feature of the EDC system is non-functional, the subject will be randomized by telephone call to the clinical coordinating center (ASTROH Project Manager). Patients should not be randomized until it is determined the patient meets all eligibility criteria, has undergone the informed consent process, AND it has been determined by the post-procedure head CT scan that the patient is still eligible to participate.

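### The deciding 90-day MoCA test is not fixed, the stratification factors and age are in no named model, and Section 10.1 misstates the strata and the centre balance

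*Protocol*

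**What the plan says.** **The MoCA test.** Section 10.1 derives Table S1 "using one-sided two-sample t test with unequal variances", with no strata or covariates, and notes that the table does not allow for covariate adjustment or for degrees of freedom spent on centres. Section 10.4 then says "MoCA will be compared between two groups using a contrast based t test in addition to simple two sample test". The model behind the contrast may be a linear regression, or a mixed model where a patient contributes several measurements. The section adds that multiple regression will be used to examine prognostic factors, without naming them.

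**Factors.** Section 10.1 lists centre, ACoA location, age (split at 70) and sex as primary factors, and fever, transfusion and vasospasm as others. ACoA location, sex and an undefined item called group are balanced by allocation. For age, "Advanced age will be controlled for by eliminating enrollment for patients over 70 years". The rest go to the multivariable model.

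**Design statements.** Section 6.4: "Finally we elected to stratify with just two factors sex and aneurysm location", with location defined as binary and site left to statistical control in the analysis. Section 10.1: "Thus, the randomization will be balanced within each of 6 strata", and "Note that we need to balance the number of treatment and controls to be equal at each center".

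**The concern.** The synopsis makes a statistically significant difference in mean 90-day MoCA one route to study success. With a simple test and a model-based contrast both planned and neither ranked, the success claim has no single deciding result.

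The model content is also the wrong way round. Section 6.4 stratifies by ACoA location because it is reported to predict cognitive disability, and Section 3 says advanced age can confound cognitive testing. Neither factor is assigned to a MoCA model. Fever, transfusion and vasospasm are assigned, yet they occur after randomisation, and Section 1.2.2 lists reducing vasospasm and changing fever as intended effects of the infusion. Conditioning on them could remove part of the treatment effect.

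The stratum count and the centre-balance sentence describe a design that Section 6.4 does not have. An analyst following Section 10.1 would not know which scheme to reflect.

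**Working it through.** **1. Reproduce Table S1.** Inputs from Section 10.1: difference 3, SDs 7.0 (control) and 2.5 (treatment), one-sided 5%, 1:1.

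- SE = √((7.0² + 2.5²)/n) = √(55.25/40) = 1.175 at n = 40.
- Noncentrality = 3/1.175 = 2.553; Satterthwaite df = 48.8; critical t = 1.677; power = 80.8%.
- The smallest n per arm for 80%, 85% and 90% is 40, 46 and 54, exactly as in Table S1.

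**2. Cost of ignoring the strata.** The protocol gives no R² for sex and ACoA location on MoCA, so a range is assumed. The calculation is a normal approximation with common SD √(55.25/2) = 5.256, n = 40 per arm and noncentrality δ = 2.553. After stratified randomisation the true SE shrinks by √(1−R²), but the unadjusted test still uses the larger SE.

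- Unadjusted one-sided error = 1 − Φ(1.645/√(1−R²)).
- Unadjusted power = 1 − Φ((1.645 − δ)/√(1−R²)).
- Adjusted power = 1 − Φ(1.645 − δ/√(1−R²)).

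| R² of strata (assumed) | Error, unadjusted | Power, unadjusted | Power, adjusted | Gain (points) |
|---|---|---|---|---|
| 0 | 5.0% | 81.8% | 81.8% | 0 |
| 0.05 | 4.6% | 82.4% | 83.5% | 1.1 |
| 0.10 | 4.1% | 83.1% | 85.2% | 2.1 |
| 0.20 | 3.3% | 84.5% | 88.7% | 4.2 |

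**3. Adding age, WFNS grade and Hijdra score.** Assume the same total R² in each arm. The slopes on a standardised covariate score are then √R² × 7.0 and √R² × 2.5. A regression with one common slope fits their average, √R² × 4.75, and so misses each arm's slope by √R² × 2.25.

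- Sum of the two residual variances = (1−R²) × 55.25 + 2R² × 2.25² = 55.25 − 45.125R².
- Power as in step 1, with these residual variances:

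| Total R² (assumed) | Variance sum | SE reduction | Power at 40 per arm |
|---|---|---|---|
| 0 | 55.25 | 0 | 80.8% |
| 0.10 | 50.74 | 4.2% | 83.7% |
| 0.20 | 46.23 | 8.5% | 86.6% |
| 0.30 | 41.71 | 13.1% | 89.5% |

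The few degrees of freedom spent on covariates are not deducted.

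**4. Strata.** Sex (2) × ACoA versus other (2) = 4. Counting group as a third binary factor gives 8. Six would need a three-level factor, and none is defined.

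**5. Centre balance.** Simulation of 8 centres of 11 patients, with permuted blocks of 4, 6, 8 or 10 within sex × ACoA only (stratum shares assumed at 15, 20, 25 and 40%): about 52% of centres differ by 3 or more patients between arms, and about 80% of trials have at least one centre differing by 5 or more. With 10 centres and random centre sizes the figures are about 37% and 67%. The scheme does not deliver equal arms per centre.

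**The case against.** Four objections deserve weight.

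- **A model is planned.** A reader might infer that MoCA will be compared only by a simple two-sample test. Section 10.4 does not support that: it plans a model-based contrast as well, and Section 6.4 promises control for site. What stands is that neither analysis is ranked.
- **Covariate lists belong in an SAP.** This is fair. Silence on the full list would be no finding, and no section bars sex, ACoA location or age from the regression. But Section 10.1 does assign factors, and the ones it sends to the model include three post-randomisation factors and exclude those used for stratification. That is stated content, and an unseen SAP does not excuse it.
- **Age.** A reader might infer that a constant age indicator will be fitted. No section proposes that; age is handled by the entry limit. What stands is that no named term covers age within 18–70.
- **Validity and size.** A reader might infer inflated type I error or a wrong sample size. Neither holds: the unadjusted test errs on the conservative side, and Table S1 reproduces exactly. Scaling both SDs by √(1−R²) would give 84%, 88% and 91% power, but that implies covariate slopes 2.8 times larger in controls (7.0/2.5), which a common-slope model cannot exploit. The lower figures in the working are the ones to use.

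**Conclusion.** The point holds in a limited form. The protocol leaves the deciding MoCA analysis open, assigns neither the stratification factors nor age within 18–70 to its model, and assigns three post-randomisation factors to it. The efficiency loss is modest: about 1 to 4 power points for the strata alone (R² 5–20%), or a rise from about 81% to about 84–90% with age, WFNS grade and Hijdra score (total R² 10–30%). Every R² here is an assumption, since the protocol gives none.

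The stratum count and the equal-arms-per-centre sentence are plain contradictions of Section 6.4. Both sit in Section 10.1. They are errors of description that do not invalidate the trial, but they should be corrected before analysis.

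**What to change.** - In Section 10.4, name as primary the treatment coefficient from a linear regression of 90-day MoCA on arm, sex, ACoA location and continuous age, optionally with WFNS grade and admission Hijdra score. Use heteroscedasticity-robust (HC3) standard errors, because the planning SDs differ so much.
- Keep the Welch t test and a site-adjusted model as sensitivity analyses.
- Keep fever, transfusion and vasospasm out of the primary model.
- In Section 10.1, change 6 strata to 4 (sex × ACoA), remove group from the balancing factors, and delete the sentence requiring equal arms at each centre.

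The cost is protocol and SAP wording and a few degrees of freedom: with 80 evaluable patients, 80 − 5 = 75 residual df for the core model, or 80 − 7 = 73 with both optional covariates. No new data are needed, and the planned enrolment is unchanged.

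### Section 10.1 sizes the trial on unequal MoCA variances, but the MoCA comparison in 10.4 does not carry that assumption over

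*Protocol*

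**What the plan says.** Protocol 10.1 bases the sample size on pilot data in which the control arm was far more variable than the heparin arm: "Because the two groups were heterogeneous, we assume SD=2.5 in treatment group and SD=7.0 in control group". Table S1 is computed "using one-sided two-sample t test with unequal variances" at alpha 5% for a 3-point difference. From it the protocol states "we plan to enroll 40 evaluable subjects in each arm", and for enrolment, "an assumed dropout rate of 10%, the trial would require 44 patients in each arm".

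Section 10.4 describes the analysis. Continuous variables get a two-sample t test or a rank sum test, and which form of t test is not said. MoCA is to be compared "using a contrast based t test in addition to simple two sample test either based on a linear regression or Mixed model approach". The sentence goes on to refer to several observations on a subject, so at least the mixed model is meant for repeated MoCA scores. No residual variance structure is given for either model.

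Two other places commit to an adjusted model. Section 6.4 leaves clinical site to statistical control in the analysis, and 10.1 sends the remaining factors to a multivariable model.

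**The concern.** The design assumes a variance ratio of 49/6.25 = 7.84 between arms. The models named in 10.4, fitted in their ordinary form, estimate a single residual variance across both arms. The standard error of the treatment contrast is then right only when the arms have the same number of evaluable patients.

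A significantly better 90-day mean MoCA is one of the two routes to the efficacy part of study success in the synopsis, so the size of this test matters. If fewer controls than LDIVH patients are evaluable, the pooled standard error is too small and the test favours heparin too often. If fewer LDIVH patients are evaluable, the standard error is too large and power is lost.

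**Working it through.** **Inputs.** From 10.1: SD 7.0 (control) and 2.5 (LDIVH), difference 3, one-sided alpha 5%, 40 evaluable and 44 enrolled per arm, 10% dropout. The evaluable splits are an assumption. Eighty are evaluable in total, and the extremes put all eight losses in one arm. Splits are written controls/LDIVH.

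**Table S1 reproduced.** At 40 per arm the standard error is sqrt(49/40 + 6.25/40) = sqrt(1.38125) = 1.175. The Satterthwaite degrees of freedom are 1.38125² / [(1.225² + 0.15625²)/39] = 48.8, and the noncentrality is 3/1.175 = 2.55. A one-sided Welch test then has power 80.8%. The smallest sizes reaching 80, 85 and 90% are 40, 46 and 54 per arm, exactly as in Table S1. Unequal variance is therefore the actual design basis.

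**Standard error of a common-variance contrast.**
- Model: sqrt{[(nC−1)·49 + (nT−1)·6.25]/(nC+nT−2) × (1/nC + 1/nT)}
- True: sqrt(49/nC + 6.25/nT)
- 40/40: 1.175 against 1.175, ratio 1.00.
- 36/44: pooled variance (35·49 + 43·6.25)/78 = 25.43. Model SE sqrt(25.43 × 0.050505) = 1.133; true SE sqrt(1.3611 + 0.1420) = 1.226; ratio 0.92.
- 44/36: pooled variance (43·49 + 35·6.25)/78 = 29.82. Model SE 1.227; true SE sqrt(1.1136 + 0.1736) = 1.135; ratio 1.08.

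**Unadjusted comparison**, normal errors, 400,000 simulated trials per setting, nominal one-sided 5%:

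| Controls/LDIVH | SE ratio | Error, pooled | Error, Welch | Rejection at 3 points, pooled | Rejection at 3 points, Welch |
|---|---|---|---|---|---|
| 40/40 | 1.00 | 5.1% | 5.0% | 81.1% | 80.8% |
| 38/42 | 0.96 | 5.8% | 5.0% | 81.6% | 79.4% |
| 36/44 | 0.92 | 6.5% | 5.0% | 81.7% | 77.7% |
| 42/38 | 1.04 | 4.5% | 5.0% | 80.8% | 82.3% |
| 44/36 | 1.08 | 3.9% | 5.0% | 79.9% | 83.3% |

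The two-sided pooled error is 7.2% at 36/44 and 3.6% at 44/36, so a 95% interval for the difference covers about 92.8% and 96.4%.

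**Adjusted comparison** (sex, ACoA, 8 sites), 6,000 simulated trials per setting. The ACoA frequency (35%) and effect (−1 point) are assumptions. The arm-specific fit was referred to a t distribution with nC−1 degrees of freedom, a simple stand-in for Satterthwaite.

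| Controls/LDIVH | Error, common variance | Error, arm-specific | Rejection at 3 points, common variance | Rejection at 3 points, arm-specific |
|---|---|---|---|---|
| 40/40 | 5.3% | 4.6% | 76.5% | 78.4% |
| 36/44 | 6.4% | 4.9% | 77.6% | 76.1% |
| 44/36 | 4.1% | 5.0% | 75.0% | 81.1% |

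Arm-specific variances gain 1.9 points of power at 40/40 and 6.1 at 44/36. At 36/44 the common-variance model rejects 1.5 points more often, but only because its error rate is inflated. HC3 robust standard errors were also tried. They were conservative (error about 4%) and less powerful (70 to 74%).

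**How likely are unequal arms?** With independent 10% loss from 44 per arm, the difference in evaluable numbers has SD sqrt(2·44·0.1·0.9) = 2.81. The chance of a gap of 4 or more in either direction is about 21%, of 6 or more about 5%, and of 8 or more under 1%. A 38/42 split is therefore ordinary, and 36/44 is extreme unless loss differs by arm.

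**The case against.** The strongest reply is that 10.4 never states a common variance. It is silent, and the residual structure and degrees-of-freedom method are commonly left to a statistical analysis plan, which is not shown here. A reader might infer that the protocol prescribes a pooled-variance analysis. It does not; pooling is the ordinary form of the methods it names. What remains is that the protocol itself chose the model class, and its ordinary form does not fit the variance assumption the protocol designed on.

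Second, the model contrast comes in addition to a simple two-sample test, and 10.1 names the unequal-variance t test. This softens the point, but 10.1 names that test as the basis of Table S1, and 10.4 does not repeat it where the analysis is set out.

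Third, the mixed model is probably meant for repeated MoCA scores. The simulations cover only the single 90-day comparison. A repeated-measures fit would also need a within-subject covariance, which was not examined.

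Fourth, allocation is blocked 1:1, dropout is monitored, and extra enrolment is considered as losses approach eight. That makes large imbalances unlikely but does not rule out moderate ones.

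Finally, a reader might infer that confidence intervals for the arm means are also wrong. Section 10.4 lists means with intervals as descriptive statistics, not model output, so the documents do not support that.

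**Conclusion.** The point holds, at modest size. The unequal-variance assumption that sets the sample size is not carried into the MoCA analysis in 10.4. If the named models are fitted in their ordinary form, the one-sided error runs from 3.9% to 6.5% across the extremes of the planned loss and is 5.8% at a plausible 38/42.

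Two stronger readings fail. The analysis is not invalid at the planned numbers, because at 40/40 the unadjusted contrast has the right standard error and loses no power. Nor is power lost in general. The loss is about 2 points at 40/40 and 6 at 44/36 in the adjusted model, and 3.4 points at 44/36 unadjusted. With fewer controls the fault is over-rejection in favour of heparin.

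These figures rest on the plan's SDs and normal errors. MoCA is capped at 30, and the control SD of 7.0 comes from 22 pilot patients, so differences of about one percentage point are indicative only.

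**What to change.** In 10.4, state two things, consistent with 10.1:

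- The simple MoCA comparison is the unequal-variance (Welch) t test.
- The MoCA regression or mixed model is fitted with a separate residual variance for each arm and Satterthwaite or Kenward-Roger degrees of freedom. In SAS this is a REPEATED statement with GROUP= set to treatment. If repeated MoCA scores are modelled, the within-subject covariance should be named in the same sentence.

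This needs no new data and no extra patients, only short wording and one model option. When fewer controls than LDIVH patients are evaluable, the rejection rate will be slightly lower than under the ordinary model (76.1% against 77.6% at 36/44, adjusted), but correctly sized.
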